4.5 Primary Safety Endpoint

The primary safety endpoint is **Inpatient safety**, which is a composite of all of following assessed upon discharge from the index hospital admission:

- (Freedom from) all-cause mortality
- (Freedom from) stroke, both disabling and non-disabling
- (Freedom from) acute coronary artery obstruction
- (Freedom from) emergency cardiac surgery or reintervention related to the TELLTALE BASILICA procedure or device
- (Freedom from) BASILICA-related complications including coronary artery perforation, coronary artery dissection, aortic dissection, cardiac free wall perforation, or systemic embolization of a native or bioprosthetic leaflet

Rationale for primary safety endpoint

The primary safety endpoint tests whether a subject tolerates attempted BASILICA using the TELLTALE guidewire. The endpoint is assessed at discharge to allow subjects to recover from general anesthesia, when required, to assess for stroke. Recovery of debris inside cerebral embolic protection devices, if employed, does not constitute systemic embolization, which is a common event after TAVR.

4.6 Secondary Endpoint: 30-day Safety

The secondary endpoint is **30-day safety**, as assessed by freedom from MACE (according to VARC-3 [30]) at 30 days, including freedom from all of the following:

- All-cause mortality
- All stroke (disabling and non-disabling)
- Bleeding VARC-3 Type 2 or greater (requiring two or more units of transfused blood or hemoglobin drop >3g/dL)
- Major vascular, access-related, or cardiac structural complication (according to VARC-3, which includes coronary obstruction)
- Acute kidney injury stage 3 or 4
- Moderate or severe aortic regurgitation
- New permanent pacemaker due to procedure-related conduction abnormalities
- Surgery or intervention related to the TELLTALE device

Rationale for secondary endpoints

The secondary endpoint is derived from a community safety standard that has recently been updated, VARC-3[30]. It is assessed at thirty-days according to VARC-3.

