9.4 Adverse Events and Serious Adverse Events

In this protocol, TAVR is clinically indicated. BASILICA using the TELLTALE Guidewire System is performed for the purpose of research.

Definition of Adverse Event

Adverse events: Any untoward medical occurrence in a human subject, including any abnormal sign (e.g., abnormal physical exam or laboratory finding), symptom, or disease, temporally associated with the subject's participation in the research, whether or not considered related to the subject's participation in the research (21 CFR 312.32 (a)).

This includes:

- Expected events related to the subject's disease process during active enrollment in the research protocol and do not directly result from use of the investigational device or study.
- Procedural events directly related to the BASILICA-TAVR cardiac catheterization procedure and recovery from the procedure and do not directly result from use of the investigational device.

Definition of Serious Adverse Events (SAE)

Serious Adverse Event (SAE): A serious adverse event that results in any of the following and NOT directly related to the device (21 CFR 812.3(s)). This includes any event that

- Results in death
- Is life-threatening (places the subject at immediate risk of death from the event as it occurs);
- results in in-patient hospitalization or prolongation of existing hospitalization;
- results in a persistent or significant incapacity;
- results in a congenital anomaly/birth defect (not relevant to this study); or
- based upon appropriate medical judgment, may jeopardize the subject's health and may require medical or surgical intervention to prevent one of the other outcomes listed in this definition.

Definition of Adverse Device Effect (ADE)

Adverse Device Effect (ADE): Any untoward or unintended response to a medical device. This definition includes any event resulting from insufficiencies or inadequacies in the instructions for use or the deployment of the device or any event that is a result of user error.

This includes procedural events directly related to the TELLTALE BASILICA procedure and recovery from the procedure in addition to use of the investigational TELLTALE devices.

Definition of Serious Adverse Device Effect (SADE), Anticipated Adverse Device Effect (AADE) and Unanticipated Adverse Device Effect (UADE)

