11.6 Clinical Events Adjudication Committee (CEAC)

An independent CEAC will review monitored data to assure accuracy. The CEAC will be an independent contractor, and the charter will be agreed between the NHLBI Principal Investigator and the CEAC after the contract is awarded, which will be after final IRB approval.

The CEAC will review all of the following events that occur in 30 days follow-up interval

- Deaths
- Primary (Efficacy) and (Safety) Endpoints
- Secondary (30-day safety) Endpoints

The CEAC will classify relatedness of the above events to the TELLTALE system devices. CEAC adjudication prevails over Principal Investigator classifications.

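### The 30-day safety component counts only device-related interventions, while the inpatient component counts procedure or device, and the adjudication committee's relatedness ruling names only the devices

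*Combined protocol and SAP*

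**What the plan says.** Two safety composites contain an intervention component, and they use different tests of relatedness.

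- Section 4.5 (primary safety, "assessed upon discharge from the index hospital admission") counts "emergency cardiac surgery or reintervention related to the TELLTALE BASILICA procedure or device".
- Section 4.6 (secondary, 30-day safety) counts "Surgery or intervention related to the TELLTALE device". The synopsis has the same wording. On the rationale, 4.6 says only that the endpoint derives from VARC-3: "It is assessed at thirty-days according to VARC-3".

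Section 11.6 lists what the CEAC reviews within 30 days: deaths, "Primary (Efficacy) and (Safety) Endpoints", and the secondary endpoint. It then adds: "The CEAC will classify relatedness of the above events to the TELLTALE system devices". Its rulings are final: "CEAC adjudication prevails over Principal Investigator classifications". No ruling on relatedness to the BASILICA procedure is specified.

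Section 9.4 does not fix what device-related means. Among adverse events that do not directly result from the device, it lists "Procedural events directly related to the BASILICA-TAVR cardiac catheterization procedure and recovery from the procedure". Its definition of an adverse device effect, however, takes in procedural events of TELLTALE BASILICA.

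**The concern.** Section 4.4 says that the efficacy endpoint tests the guidewire and not the BASILICA procedure. Harm from the procedure therefore has to show up in the safety endpoints. Section 4.3 describes how that harm arises when the wire has done its job: a badly oriented slice, or leaflet material that protrudes into a coronary artery and needs a stent. An adjudicator could fairly call such an event procedure-related and not device-related.

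Under 4.5 that distinction makes no difference. Under 4.6 it decides whether the intervention component is failed. The same inpatient event can then fail the intervention component at discharge and pass it at 30 days, although the later endpoint would be expected to contain the earlier event. The 30-day composite is also reused: at 90 days as an exploratory endpoint (4.7), and in the subgroup analyses and the exploratory comparison with the earlier BASILICA IDE study (10.4).

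**Working it through.** No figure in the plan is at issue, so the check is a comparison of the texts, followed by the size of one misplaced event.

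**Step 1. The two components side by side**

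| | 4.5 primary safety | 4.6 secondary safety |
|---|---|---|
| Window | index admission | 30 days |
| Related to | BASILICA procedure or device | device |
| Relatedness ruling specified in 11.6 | devices only | devices only |
| Components with no device test | death, stroke, coronary obstruction, BASILICA-related perforation, dissection or leaflet embolization | death, stroke, bleeding, major vascular, access or cardiac structural complication (including coronary obstruction), kidney injury, aortic regurgitation, pacemaker |

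**Step 2. Trace four events through the definitions**

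1. Inpatient emergency cardiac surgery, procedure-related, ruled not device-related, no other component met: fails 4.5, passes 4.6.
2. Slice malorientation or leaflet prolapse that obstructs a coronary artery in hospital: fails both through coronary obstruction. No relatedness test applies.
3. Cautionary stenting without obstruction (a category named in 4.7), ruled procedure-related but not device-related, no other component met: passes 4.6. It is recorded as exploratory. Whether it fails 4.5 depends on whether it is a reintervention, which 4.5 does not define.
4. Procedure-related intervention after discharge and within 30 days, ruled not device-related, no other component met: outside the window of 4.5 and outside the wording of 4.6, so in neither endpoint.

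Events 1, 3 and 4 are the gap. Only event 4 is necessarily missing from both endpoints.

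**Step 3. Size of one event**

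Input: 90 subjects with an attempt (10.2).

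- Each omitted subject changes the 30-day rate by 1/90 = 1.1 points, or by nothing if the subject fails another component.
- In the native subgroup, at its quota of 30, the change is at most 1/30 = 3.3 points.

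The plan asks for a 95% interval without naming a method (10.4). Exact (Clopper-Pearson) intervals, for illustration:

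| Events restored | Freedom if no other failures | Freedom from an assumed 70% (63/90) |
|---|---|---|
| 0 | 100% (96.0 to 100) | 70.0% (59.4 to 79.2) |
| 1 | 98.9% (94.0 to 99.97) | 68.9% (58.3 to 78.2) |
| 2 | 97.8% (92.2 to 99.7) | 67.8% (57.1 to 77.2) |
| 3 | 96.7% (90.6 to 99.3) | 66.7% (55.9 to 76.3) |

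The 70% is borrowed from the earlier IDE study (21 of 30 free of MACE, section 3.2).

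**Step 4. How many events**

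The documents give no rate for interventions that are procedure-related only. If that rate were 0.5% to 3% (an assumption), the expected number is 90 × 0.005 = 0.45 to 90 × 0.03 = 2.7 subjects.

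**The case against.** The strongest reply has three parts.

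*Device may already include the procedure.* The adverse-device-effect definition in 9.4 covers BASILICA procedural events, which would close most of the gap. This does not settle the matter. It defines a reporting category and not an endpoint, and 9.4 elsewhere separates procedural from device events. The phrase in 4.5 would be redundant if device meant both, and 4.6 itself uses procedure-related wording for pacemakers and device wording for its last item. Two adjudicators could rule differently.

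*Most procedural harm counts anyway.* This stands. Coronary obstruction, structural and vascular complications, bleeding and aortic regurgitation fail 4.6 without any device test. Section 5.4 also argues that BASILICA complications are not expected after discharge, which makes event 4 unlikely on the plan's own view.

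*Nothing is decided by it.* This also stands. Sections 10.1 and 10.4 set no hypothesis or performance goal, and a different scope at 30 days could be deliberate. No reason for it is given, however.

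Three stronger readings are tempting, and the documents do not support them.

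- A reader might infer that procedure-related reinterventions drop out of both endpoints. Section 4.5 counts the inpatient ones expressly, and nothing says that a ruling of not device-related cancels such an event.
- A reader might infer that the procedure judgement is left to the unblinded investigator. Sections 9.3, 11.6 and 11.16 all put the primary endpoints before the independent committee. What is missing is a specified procedure classification, not adjudication.
- A reader might scale up the European registry in 3.2: 10 of 76 needed coronary intervention, and 9% of 76, about 7, were obstructed. At least 3 of 76 then had an intervention without obstruction, and 3/76 × 90 = 3.6. That registry used off-the-shelf devices and included 12% double-leaflet cases, which are excluded here. It does not show the attribution of these events, their timing, or whether they would meet another component. The earlier IDE study reported no coronary obstruction or reintervention in 30 subjects. No count of affected subjects can be taken from these figures.

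**Conclusion.** The inconsistency is real and of minor severity. Section 4.6 and the synopsis omit interventions related to the BASILICA procedure that are judged not device-related and meet no other component. Section 11.6 does not specify the procedure ruling that 4.5 needs. The loss is from the 30-day endpoint. It extends to both endpoints only for such an event after discharge and within 30 days.

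The effect is at most 1.1 points on the 30-day rate per affected subject, always in the favourable direction, and the number of such subjects cannot be derived from the documents. The conclusion assumes that device is read in its narrow sense. If the CEAC charter, which is not part of these documents, already treats procedure and device together, the correction only makes that explicit.

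**What to change.** 1. In 4.6 and the synopsis, extend the last component so that it names the TELLTALE BASILICA procedure or device, the same relatedness phrase as in 4.5.
2. In 11.6, have the CEAC classify relatedness to the device and, separately, to the BASILICA procedure, and score the component as failed if either applies. A separate classification for TAVR is optional.

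The cost is one phrase in two places, one sentence, and one field on the adjudication form. The same committee reviews the same events. The one downside is that the 30-day safety rate may be slightly less favourable.

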4.7 Exploratory Endpoints

- Primary and secondary endpoints among subjects with native versus bioprosthetic disease
- Stroke: disabling and non-disabling
- Coronary stenting: snorkel (heterotopic) and orthotopic (through TAVR stent cells), to prevent or treat leaflet-induced coronary obstruction before (preemptive) and after (bailout or cautionary) TAVR.
- Facilitated BASILICA procedure success, as defined in section 0.
- Composite safety (secondary endpoint) assessed at 90 days
- Ability selectively to engage threatened coronary ostia after BASILICA-TAVR
- Acute hemodynamic deterioration in the interval between BASILICA and TAVR
- Outcomes of subjects who participate in live case demonstrations compared with those who do not

Rationale for Exploratory Endpoints

Coronary stenting related to leaflet obstruction is undesirable and may reflect failed or aborted BASILICA, typically in the heterotopic (“snorkel”) position. Orthotopic coronary stenting is

typically required to treat leaflet prolapse related to mechanical avulsion manifest typically as severe acute aortic regurgitation with hemodynamic compromise.

TAVR can render coronary arteries inaccessible for later emergency PCI. We will capture the ability to selectively engage coronary arteries after BASILICA-TAVR.

5 STUDY DESIGN

5.1 Constant values

Number of subjects	90
Number of subjects with native aortic valve failure, initially	15
Number of additional subjects with native aortic valve failure invited to participate as part of study expansion	15
Maximum number of subjects with native aortic valve failure	30
Number of candidates screened, up to	180
Number of enrollment sites	15
Follow-up duration per subject	90 days
Expected study duration	12 months for enrollment + follow-up

5.2 Overall Design

This is a prospective, open-label, single-arm, multi-center, independently-adjudicated investigation of BASILICA (Bioprosthetic or native Aortic Scallop Intentional Laceration to prevent Coronary Artery obstruction) using the Transmural TELLTALE guidewire system immediately before TAVR (transcatheter aortic valve replacement) in subjects at high risk of coronary artery obstruction, as defined in the selection criteria.

NHLBI Division of Intramural Research is the data coordinating center. Subjects undergo the study intervention only at enrolling centers.

5.3 Scientific Justification for Initiating this Study

The purpose of the study is prospectively to evaluate the safety and efficacy of BASILICA-TAVR performed with the TELLTALE guidewire system.

Because coronary artery obstruction is a predictable and life-threatening complication, because pre-emptive “snorkel” stenting is considered an inappropriate and undesirable strategy, because subjects are not good candidates for alternative surgical aortic valve replacement treatment, and because the study devices are considered intrinsically superior to bedside-modified commercial devices used for standard BASILICA, there is no control arm in this investigation.

The study is intended to support commercialization of the TELLTALE Guidewire System. We believe the study objectives cannot be met *in vitro*, using cadaver or surgical specimens *ex vivo*, nor using naïve or diseased animal models *in vivo*. Moreover, this study offers the prospect of direct benefit to subjects. Therefore clinical evaluation is reasonable.

5.4 Scientific Justification for Duration of Study Follow-up

The complications of BASILICA are evident upon procedure conclusion. Out of caution, adverse events are assessed upon hospital discharge and again after 30 days.

In the prospective BASILICA IDE trial, using “off-label” bedside modification of commercially available catheter tools, there were no new adverse events that could be attributed specifically to BASILICA after 30 days. Specifically, there were no new thrombotic events (no stroke, no MI, no coronary obstruction, no transcatheter aortic valve failure, no increase in valve gradients), the coronaries remained clinically patent, no heart failure admissions, and no BASILICA related deaths.

Moreover, we do not believe there is a plausible scientific rationale to suspect adverse events after discharge. In native and valve-in-valve TAVR, the prior valve tissue is disrupted and distorted by TAVR implantation. BASILICA does not significantly alter this disruption.

It is not clear whether BASILICA increases the risk of stroke compared historically against TAVR without BASILICA. Neurological events were identified in our early prospective BASILICA IDE trial (n=30) [3, 24] but not evident in the non-adjudicated BASILICA registry (n=213) [4]. We do not believe BASILICA-related strokes occur after hospital discharge. Moreover, the “Protected TAVR” trial [NCT04149535] of TAVR stroke prevention using the Sentinel Cerebral Protection System (Boston Scientific), has a primary endpoint of “All stroke (hemorrhagic, ischemic, or undetermined status; disabling or nondisabling) through 72 hours post TAVR procedure or discharge.”

Based on feedback from FDA CDRH, we plan a final follow-up encounter, remote or in-person, at 90 days.

5.5 Justification for single-arm study design

We do not believe there is an appropriate comparator group for BASILICA TAVR using the TELLTALE guidewire.

First, redo surgical aortic valve replacement appears to have higher risk of death, major bleeding, or prolonged hospital stay than valve-in-valve TAVR in general, among both intermediate and higher risk patients (Summarized in a recent meta-analysis [31]). Therefore surgical therapy is not an appropriate comparator, especially among high- or prohibitive-risk subjects.

Second, we do not believe “snorkel stenting” is appropriate therapy or prophylaxis for patients at risk for acute TAVR-associated coronary obstruction. Snorkel stenting is “off-label,” the devices lack sufficient radial strength to separate the TAVR from the wall of the aortic root or sinotubular junction, coronary stents in this heterotopic position risk deformation and thrombosis, expose the patient to prolonged or indefinite antiplatelet and antithrombotic pharmacotherapy with attendant bleeding risk, and interfere with safe future re-access to the coronary arteries for PCI. We do not endorse snorkel stenting for any patient when BASILICA or surgery is an option.

Third, we believe many candidates are offered no definitive therapy for aortic valve stenosis or bioprosthetic valve failure when they are at high risk of coronary obstruction. We attribute this un-documented phenomenon to operator inexperience and the recent guidance provided to transcatheter heart valve manufacturers that BASILICA proctorship may be construed as inappropriate marketing. Part of our motivation to develop the TELLTALE guidewire system is to empower industry-supported proctors and operators to offer BASILICA when needed by their patients.

Absent standard of care for patients at risk of TAVR-induced coronary obstruction and at high or prohibitive risk of surgical aortic valve replacement, we are unable to identify a suitable comparator group. Among our clinical investigation group, several physicians believe randomization to surgery or snorkel-stenting to be unethical.

6 STUDY POPULATION

6.1 Inclusion Criteria

In order to be eligible to participate in the study, candidates must meet all of the following criteria:

- Adults age \geq 21 years
- High or prohibitive risk of surgical aortic valve replacement according to the local multidisciplinary heart team
- Undergoing TAVR for bioprosthetic aortic valve failure or native aortic stenosis (“on-label” TAVR)
- Local multidisciplinary heart team determines subject to be at high risk of TAVR-induced coronary artery obstruction
- Deemed likely to suffer coronary artery obstruction from TAVR based on NHLBI Core lab analysis of CT, any of
 - Risk is narrow Sinus of Valsalva: (a) Leaflet height is greater than coronary artery height, and (b) Virtual transcatheter valve-to-coronary (VTC) distance $< 4\text{mm}$
 - Risk is Sinus sequestration: (a) Threatening leaflet height is greater than sinotubular junction, and (b) Virtual transcatheter valve-to-sinotubular-junction distance (VTS) $< 2\text{mm}$ at the affected Sinus
- Concurrence of the Study Eligibility Committee
- Able to understand the protocol, consents in writing to participate, and willing to comply with all study procedures for the duration of the study

6.2 Exclusion Criteria

- Requires doppio (two-leaflet) BASILICA
- Flail target leaflet at baseline
- Excessive target aortic leaflet calcification (no basal calcium-free window or potentially obstructive calcific masses) on baseline CT
- Planned provisional (pre-position coronary artery) stents despite BASILICA
- Requires non-femoral access
- Requires concomitant procedures during TAVR (such as percutaneous coronary intervention for baseline obstructive coronary artery disease)
- Chronic kidney disease KDIGO stage 4 or 5 (eGFR < 29 ml/min/1.73m²) or renal replacement therapy
- Not expected to survive for 12 months
- Pregnant at the time of intended treatment (day 0)

6.3 Enrollment Quota

A subset of subjects will have native aortic valve failure (initially n=15). Sequential enrollment will accommodate this quota. A "study expansion" IDE amendment increased this quota from 15 to a maximum 30.

6.4 Rationale for selection criteria

The selection criteria allow enrollment of the intended population with little anticipated selection bias.

Children are excluded because children in general are not eligible for transcatheter aortic valve replacement. There is no maximum eligibility age because there is no scientific basis for age-based exclusion *per se*.

The CT criteria for anatomic eligibility based on valve-to-coronary distance and valve-to-sinus distance are based on prior reports [2] and experience [3].

Excessive target leaflet calcification can exclude candidates from BASILICA based on two criteria:

- (1) Confluent leaflet calcification on CT at the intended basal traversal target reduces the likelihood of successful electrosurgical leaflet traversal. Conversely, any size calcium-free window at the leaflet traversal target will allow successful electrosurgical traversal.
- (2) Calcific masses, defined as aortic native or bioprosthetic leaflet masses that, if displaced centrifugally by TAVR, are predicted by CT ("displacement/rotation along the hinge point") to obstruct coronary artery ostia by "mass effect." Such pathology is not amenable to BASILICA [5].

Subjects are eligible if they are at high or prohibitive risk of surgical aortic valve replacement based on two randomized clinical trials, with two different transcatheter heart valves, that showed non-inferiority of TAVR versus surgical aortic valve replacement [32, 33].

Flail baseline leaflet is excluded because of risk of leaflet prolapse after successful traversal and laceration [35]. Excessive leaflet calcification is excluded because it prohibits traversal, or when

it risks coronary obstruction through a mechanism (such as mass) not amenable to prevention by BASILICA.

Concomitant procedures might induce complications that confound assessment of TELLTALE-related complications, and are therefore excluded. Non-femoral access is associated with a higher risk of complications and such candidates are therefore excluded.

Pregnant candidates are excluded because they are generally excluded from elective transcatheter aortic valve replacement. Contraception is not required of subjects because research-related radiation is confined to the chest and only occurs on study day 0.

Cognitively-impaired candidates are excluded based on our experience with inability to comply with quality-of-life questionnaire instruments, and frequent unwillingness to return for follow-up after TAVR in protocols such as this one.

The inclusive selection criteria and geographic extent of enrolling sites are expected to allow recruitment of a diverse economic, ethnic, and racial mix of patients that reflects the incident disease.

Doppio BASILICA is excluded because discordant first and second leaflet results would impact assessment of the primary efficacy endpoint. [\[34\]](#)[\[34\]](#)[\[4\]](#)[\[25\]](#)

